1.2. Study Objectives

Primary:

To evaluate the anti-tumor efficacy of trilaciclib when administered prior to sacituzumab govitecan-hziy as measured by progression free survival (PFS).

Secondary:

To evaluate the anti-tumor efficacy of trilaciclib administered prior to sacituzumab govitecanhziy as measured by the objective response rate (ORR), duration of objective response (DOR), clinical benefit rate (CBR), and overall survival (OS); evaluate the myeloprotective effects of trilaciclib; and assess the safety and tolerability of trilaciclib administered prior to sacituzumab govitecan-hziy.

Specifically, the primary and secondary objectives and their associated endpoints are described in Table 1.

Objectives	Endpoints	
Primary Objective		
To evaluate the anti-tumor activity of trilaciclib when administered prior to sacituzumab govitecan-hziy	• PFS defined as time from the date of first dose of study drug to radiographic disease progression using RECIST v1.1 or death due to any cause, whichever occurs first; for patients without disease progression or death, PFS will be calculated per censoring rules.	
Secondary Objective: Efficacy		
To evaluate the anti-tumor activity of trilaciclib when administered prior to sacituzumab govitecan-hziy	 ORR defined as the percentage of patients with BOR of confirmed CR or confirmed PR per RECIST v1.1 CBR defined as the percentage of patients with a BOR of confirmed CR, confirmed PR, or SD lasting 24 weeks or longer since the first date of study drug administration per RECIST v1.1 DOR defined as duration of objective response OS defined as time from the date of first dose of study drug to death due to any cause for those who died; or time to last contact known as alive for those who survived in the study (censored cases) 	
Secondary Objective: Myeloprotective eff	fects of trilaciclib	
• To evaluate the myeloprotective effects of trilaciclib when administered prior to sacituzumab govitecan-hziy	 Occurrence of SN (during Cycles 1/2 and overall study) Occurrence of febrile neutropenia Occurrence of G-CSF administration 	

Table 1Primary and Secondary Objectives and Endpoints

Objectives	Endpoints	
Secondary chiestiyes: Sefety	 Occurrence of Grade 3/4 decrease of hemoglobin Occurrence and number of RBC transfusions on/after Week 5 Occurrence of ESA administration Occurrence of Grade 3/4 decrease of platelets Occurrence and number of platelet transfusions Occurrence of serious infections Use of IV antibiotics 	

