8. EFFICACY ANALYSIS

All efficacy analyses will be performed for the FAS population, unless specified otherwise.

The primary efficacy endpoint for this study is the treatment effects on PFS. PFS and other efficacy endpoints related to tumor response (ORR, CBR, and DOR) and myeloprotection efficacy will also be evaluated based on data collected during the treatment period (see Section 2.1).

The treatment effect on OS will be evaluated when the number of events specified in Section 2.1 are observed for OS. The clinical database will be locked for this analysis. At the time of the final planned analysis, all other efficacy analyses outlined for the study will also be conducted.

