8.1. Definitions of Efficacy Endpoints

8.1.1. Primary Efficacy Endpoints – Progression Free Survival

Progressive disease (PD) and tumor response status are programmatically determined according to RECIST v1.1 based on the radiographic tumor assessment data recorded on the eCRF by the Investigator for target lesions, the investigator assessment of non-target lesions, and the status of new lesions. For a patient, the status of PD will be determined using all radiographic tumor scan data assessed prior to or on the date of the data cutoff to conduct the analysis for PFS. In the situation where PD and withdrawal of consent or PD and initiation of subsequent anticancer therapy occurred on the same day for a patient, the PD status will be assumed for that patient.

Radiographic PD and death due to any cause during the study are referred to as PFS events.

PFS is defined as the time (months) from date of C1D1 to the date of the first documented disease progression, or death in the absence of PD for those who had a PFS event, and the time from date of C1D1 to the censoring date for those who did not have a PFS event. Specifically, PFS is calculated as (date of PFS event or censoring – date of C1D1+ 1)/ 30.4375. The analysis for PFS will be based on the FAS.

Details for PFS calculation and censoring rules can be found in Table 6.

Situation	Date of Event or Censoring	Outcome
Disease progression per RECIST Version 1.1	Date of the first documented progression	PFS event
Death without a PD	Date of death	PFS event
Incomplete or no baseline tumor assessments	Date of C1D1	Censored
No progression	Date of the last adequate radiological tumor assessment with no documented disease progression	Censored
Treatment discontinuation for reasons other than disease progression	Date of the last adequate radiological tumor assessment with no documented progression	Censored
Subsequent anticancer treatment started prior to documented disease progression	Date of last adequate radiologic assessment prior to or the date of initiation of subsequent anticancer treatment	Censored

Table 6PFS Calculation and Censoring Rules

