8.1.2. Secondary Efficacy Endpoint – Anti-tumor Efficacy Endpoints

The secondary anti-tumor endpoints include the following, which will be calculated and reported at the final analysis:

- Best overall response (BOR)
- Objective response rate (ORR)
- Clinical benefit rate (CBR)
- Duration of confirmed objective response (DOR)

The analysis of these endpoints will be based on the RE population. Tumor scan data collected during the study will be the basis to classify tumor response status for patients in the RE population.

At each tumor assessment visit, an overall timepoint response by RECIST v1.1 will be determined programmatically using the measurements recorded on the eCRF by the Investigator for target lesions, the Investigator assessment of non-target lesions, and records of new lesions.

If a patient has all or some of the following records prior to the final database lock, the earliest date of those will be used to determine the inclusion of tumor scan data for response status derivation: (i) radiographic disease progression; (ii) withdrawal of consent to obtain scans; (iii) death; (iv) lost to follow-up; or (v) initiation of subsequent anticancer therapy.

Best Overall Response

BOR categorizes a patient's tumor response status into one of following mutually exclusive categories per RECIST v1.1: Complete Response (CR), Partial Response (PR), Stable Disease (SD), Progressive Disease (PD), and Not Evaluable (NE). The minimum duration of stable disease must be 5 weeks starting from the date of Cycle 1 Day 1 (the protocol scheduled tumor assessments is every 6 weeks for the first 36 weeks following Cycle 1 Day 1 (\pm 7 days) and every 9 weeks thereafter (\pm 7 days)).

Objective Response Rate

Achieving an objective response for a patient is defined as having a CR or PR as the BOR. Objective response rate is defined as the proportion of the patients who achieved objective response on the RE population.

Confirmed Objective Response Rate

Confirmed CR or PR will be derived based on the principle described in RECIST v1.1. In the derivation, the minimum interval for confirmation of CR or PR is 4 weeks, and the minimum duration of treatment is 5 weeks (the protocol scheduled tumor assessments is every 6 weeks for the first 36 weeks following Cycle 1 Day 1 (\pm 7 days) and every 9 weeks thereafter (\pm 7 days)). Confirmed ORR (confirmed CR or PR) is defined as the proportion of the patients who achieved confirmed objective response.

Clinical Benefit Rate

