9. SAFETY ANALYSIS

9.1. General Consideration of Safety Analysis

Safety data summaries will be based on the safety population as defined in Section 3.3 of this SAP.

Safety data collected during treatment will be summarized at the final analysis.

Safety and tolerability will be assessed by AEs, laboratory tests, vital signs and ECG. Safety data will be summarized using descriptive statistics for all patients when appropriate. All safety data collected through scheduled and non-scheduled visits during the treatment period will be included in the safety data analyses. The treatment period for a patient is defined as the time interval from date of C1D1 to the date of End of Treatment (EOT) visit. If the EOT visit does not occur for the patient, then 14 days post the last dose in the last cycle will be used as the end date of treatment. Missing safety data will generally not be imputed, unless otherwise specified.

Baseline assessment is, in general, defined as the last non-missing observation prior to receiving the first dose of any study drug.

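### SAP Table 6 censors PFS when treatment stops without progression and does not exempt patients who later progress or die, so the SAP contradicts itself on which events count for PFS and DOR

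*SAP*

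**What the plan says.** **The row.** SAP 8.1.1, Table 6, has two event rows: RECIST progression, and death without progression. A further row, "Treatment discontinuation for reasons other than disease progression", has the outcome Censored, dated to the last adequate scan that shows no progression. It does not mention later progression or death.

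**SAP text for counting later events.**
- Table 1 (SAP 1.2): "for patients without disease progression or death, PFS will be calculated per censoring rules".
- SAP 8.1.1 gives a censoring time only as the time to "the censoring date for those who did not have a PFS event".
- SAP 8.1.1 also says that "the status of PD will be determined using all radiographic tumor scan data assessed prior to or on the date of the data cutoff".
- For response, SAP 8.1.2 says: "Tumor scan data collected during the study will be the basis to classify tumor response status for patients in the RE population". Its list of cut-offs for scan data does not include stopping treatment.

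**SAP text pointing the other way.**
- SAP 8 says that PFS, ORR, CBR and DOR "will also be evaluated based on data collected during the treatment period". It refers to Section 2.1, which sets analysis timing and defines no data window.
- The only definition of the treatment period is in the safety section (SAP 9.1): "defined as the time interval from date of C1D1 to the date of End of Treatment (EOT) visit", or 14 days after the last dose if that visit does not occur.

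**The protocol.** Section 12.4.6.1 always counts death without progression as a PFS event. It does not list stopping drug as a cut-off, and it leaves to the SAP only the censoring of patients without progression or death at cutoff. The DOR censoring list in 12.4.6.2 has consent withdrawal, loss to follow-up and new anticancer therapy. Sections 10.1 and 11.2.1 continue scans after treatment stops.

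**Precedence.** SAP 8.1.2 applies the Table 6 censoring rules to DOR. SAP 1 states that the SAP overrides the protocol. SAP 10 declares no change on this point.

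**The concern.** A patient who stops for toxicity and then progresses or dies before any new therapy fits both an event row and the discontinuation row. Two programmers working from the same SAP could therefore derive different primary results.

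If the discontinuation row wins, those events leave both PFS and DOR. The trial has one arm and its reference is a historical median of 5.6 months, so a shift in the derived median is not cancelled by a control arm. SAP 8.2.2 plans Kaplan-Meier quantiles and landmark rates but no PFS test. What is at stake is therefore the reported median, the 12-, 18- and 24-month rates and DOR, not a test decision.

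**Working it through.** **1. The plan's own figures.** Inputs from Protocol 12.1: N = 45, accrual a = 10 months, follow-up f = 14 months, exponential PFS, control median 5.6, two-sided alpha 0.20.

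Expected events: E = N × [1 − (e^(−λf) − e^(−λ(f+a))) / (aλ)].

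- For HR 0.70, λ = 0.7 × ln 2 / 5.6 = 0.0866, so E = 45 × [1 − (0.2973 − 0.1250) / 0.866] = 36.05.
- For HR 0.80, E = 37.86.
- Power by the simple formula Φ(√E × |ln HR| − 1.2816) is 0.805 and 0.536. With the exact variance under the alternative it is 0.795 and 0.536.

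The plan states 36 events and 80%, and 38 events and 54%. Its figures reproduce and are not in dispute. At the final N = 30 the same formula gives 24.0 events (median 8.0) or 27.0 (median 5.6).

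**2. The rows side by side.** Take a patient who stops for toxicity and has progression on a later scan, with no new therapy.

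| Text | Result |
|---|---|
| Table 6, progression row | Event |
| Table 6, discontinuation row | Censored |
| SAP Table 1 and 8.1.1 narrative | Event |
| SAP 8 with the 9.1 period | Later scan is outside the window |
| Protocol 12.4.6.1 | Event |

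**3. Events lost if the row is applied literally, equal hazard.** The share p who stop before progression is not in the documents; 20% is assumed. Stopping hazard = λp/(1 − p) = 0.25λ. With λ = ln 2 / 5.6 = 0.1238, the combined hazard is 1.25λ = 0.1547.

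Events kept = 30 × 0.8 × [1 − (e^(−0.1547×14) − e^(−0.1547×24)) / 1.547] = 24 × [1 − (0.1146 − 0.0244) / 1.547] = 22.6.

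Lost: 27.0 − 22.6 = 4.4.

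**4. Shift in the median, by simulation.** There were 1,000,000 patients per scenario, with 20% stopping, censoring uniform on 14 to 24 months, and scans every 6 weeks to week 36, then every 9. The later hazard is 1, 2 or 3 times the on-treatment hazard. Stoppers who start new therapy are censored under every reading. The comparison is with counting the later event; events are per 30 patients. The row can be dated in two ways, so both are shown.

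| Scenario | Events lost | Shift, last progression-free scan | Shift, last scan before stopping |
|---|---|---|---|
| Base 5.6, no new therapy | 4.4, 5.2, 5.4 of 27 to 28 | +0.50, +0.68, +0.78 | −0.11, +0.22, +0.42 |
| Base 5.6, half on new therapy | 2.2, 2.6, 2.7 of about 25 | +0.23, +0.35, +0.42 | −0.06, +0.13, +0.24 |
| Base 8.0, no new therapy | 3.2, 4.3, 4.7 of 24 to 25.5 | +0.73, +1.01, +1.15 | about −0.1, +0.36, +0.64 |

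The first dating follows the row's wording, which qualifies the scan by absence of progression and not by its timing relative to stopping. Because scans continue, that scan may fall just before the event. The patient then keeps nearly all event-free time and loses only the event, so the median rises even at equal hazard. The second dating needs a window taken from SAP 8 and 9.1. At equal hazard it lowers the median slightly, because it discards event-free time between the last scan and stopping.

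**5. Scale.** The sampling SD of a 30-patient median at base 5.6 is about 1.3 to 1.6 months, larger than any shift in the table.

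**The case against.** The best defence is that the governing definition already settles the matter. SAP 8.1.1 defines the events, reserves a censoring date for patients without one, and offers Table 6 only as detail. Protocol 12.4.6.1 delegates to the SAP only the censoring of event-free patients. SAP 8.2.2 asks for reasons for censoring, so a row that merely labels a reason has a use. SAP 8.1.1 sets same-day tie-breaks for consent withdrawal and for new therapy but none for stopping treatment. The treatment-period definition belongs to the safety section, and the specific PFS text should prevail over the general sentence in SAP 8.

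Most of this stands: counting later events is the better-supported reading. It does not close the question, for two reasons.
- The adjacent row, "Subsequent anticancer treatment started prior to documented disease progression", does override a later progression under the same general text, so event rows do not always win in this table. It is true that this row states its time limit and the discontinuation row does not. A reader still has to infer the difference.
- SAP 8 names PFS and DOR in the sentence on treatment-period data, and nothing corrects it.

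A reader might infer that the analysis will drop these events, or that the reported PFS will be biased upward. The documents support neither. The first depends on a reading that the SAP's own narrative disfavours. The second depends on which scan date is used, on the later hazard, and on how many stoppers start new therapy first.

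**Conclusion.** The point holds as a contradiction inside the SAP about the event rule for the primary endpoint and DOR. The row as written, and the treatment-period sentence in SAP 8, conflict with Protocol 12.4.6.1 and 12.4.6.2, and the change is undeclared. It should be fixed, but it does not show that results will be wrong.

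If the row were applied literally, about 2 to 5 events per 30 patients would be lost at 20% stopping and base median 5.6. The median would move by between −0.11 and +0.78 months, depending on censoring date, later hazard and new therapy. At base 8.0 with no new therapy, the range is about −0.1 to +1.15.

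The share stopping, the later hazard and the share on new therapy are assumptions. Follow-up of 14 to 24 months comes from the 45-patient plan, whereas SAP 2.1 now times the analysis at 21 deaths among 30. A longer scan interval after stopping, such as the 12 weeks in Protocol 10.1, was not modelled.

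It would also be wrong to infer that the stated power or event counts are faulty, or that a decision could flip: those figures reproduce, and no PFS test is planned.

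**What to change.** - In Table 6, delete the discontinuation row, or restrict it to patients with no progression or death by data cutoff so that it serves only as a censoring reason.
- State that progression or death before subsequent anticancer therapy is an event at its actual date, for PFS and DOR, whether or not treatment has stopped.
- In SAP 8, for PFS and DOR, replace the reference to the treatment period with data up to the cutoff.
- If a discontinuation-censored version is wanted, report it as a sensitivity analysis only, and state which scan sets the censoring date.

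The cost is a small change of SAP wording and, if the sensitivity analysis is kept, one extra run on data already collected. The downside is that the reported median may be slightly less favourable than under the literal row.

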8.1.2. Secondary Efficacy Endpoint – Anti-tumor Efficacy Endpoints

The secondary anti-tumor endpoints include the following, which will be calculated and reported at the final analysis:

- Best overall response (BOR)
- Objective response rate (ORR)
- Clinical benefit rate (CBR)
- Duration of confirmed objective response (DOR)

The analysis of these endpoints will be based on the RE population. Tumor scan data collected during the study will be the basis to classify tumor response status for patients in the RE population.

At each tumor assessment visit, an overall timepoint response by RECIST v1.1 will be determined programmatically using the measurements recorded on the eCRF by the Investigator for target lesions, the Investigator assessment of non-target lesions, and records of new lesions.

If a patient has all or some of the following records prior to the final database lock, the earliest date of those will be used to determine the inclusion of tumor scan data for response status derivation: (i) radiographic disease progression; (ii) withdrawal of consent to obtain scans; (iii) death; (iv) lost to follow-up; or (v) initiation of subsequent anticancer therapy.

Best Overall Response

BOR categorizes a patient's tumor response status into one of following mutually exclusive categories per RECIST v1.1: Complete Response (CR), Partial Response (PR), Stable Disease (SD), Progressive Disease (PD), and Not Evaluable (NE). The minimum duration of stable disease must be 5 weeks starting from the date of Cycle 1 Day 1 (the protocol scheduled tumor assessments is every 6 weeks for the first 36 weeks following Cycle 1 Day 1 (\pm 7 days) and every 9 weeks thereafter (\pm 7 days)).

Objective Response Rate

Achieving an objective response for a patient is defined as having a CR or PR as the BOR. Objective response rate is defined as the proportion of the patients who achieved objective response on the RE population.

Confirmed Objective Response Rate

Confirmed CR or PR will be derived based on the principle described in RECIST v1.1. In the derivation, the minimum interval for confirmation of CR or PR is 4 weeks, and the minimum duration of treatment is 5 weeks (the protocol scheduled tumor assessments is every 6 weeks for the first 36 weeks following Cycle 1 Day 1 (\pm 7 days) and every 9 weeks thereafter (\pm 7 days)). Confirmed ORR (confirmed CR or PR) is defined as the proportion of the patients who achieved confirmed objective response.

Clinical Benefit Rate

Clinical benefit rate is defined as the proportion of patients with BOR of confirmed CR, confirmed PR, or SD lasting 24 weeks or longer, based on the RE population.

Duration of Confirmed Objective Response

DOR is calculated for patients who achieved confirmed CR or PR as the BOR status. It is defined as the time (months) from the date when the objective response of CR or PR was first documented to the date that radiographic progressive disease is documented, or death, whichever comes first. That is, DOR = (Date of documented disease progression or death – date of first documented CR or PR + 1)/30.4375.

Censored DOR follows the same rules as the censoring rules for PFS (see Table 6).

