# Statistical analysis methods for primary and secondary endpoints

Analysis for primary efficacy endpoint

The primary endpoint, PFS, is defined as the time (months) from the date of first dose of study drug until the date of documented radiographic disease progression (PD) per RECIST v1.1 or death due to any cause, whichever comes first. For patients who do not experience PD or are alive at the time of performing the analysis, PFS will be calculated per censoring rules detailed in the Statistical Analysis Plan. The primary analysis for PFS will be conducted at the time when 36 patients have radiographically-determined disease progression or have died. A Kaplan-Meier plot will be produced. The median, 25th percentile, and 75th percentile of PFS will be estimated using the Kaplan-Meier method with their corresponding 95% confidence internal (CI) calculated based on the method by Brookmeyer and Crowley (1982). PFS will be analyzed on the FAS population.

Analysis for secondary anti-tumor efficacy endpoints:

Tumor response:

Objective response rate is defined as the proportion of patients with best overall response (BOR) of either confirmed complete response (CR) or confirmed partial response (PR) per RECIST v1.1. ORR, along with its 95% two-sided CI using the Clopper-Pearson method, will be computed. ORR will be analyzed on the RE population.

CBR is defined as the proportion of patients with a BOR of confirmed CR, confirmed PR, or stable disease lasting 24 weeks or longer from the first date of study drug administration. CBR will be analyzed similarly as ORR based on the RE population.

DOR is the time (months) between the date of achieving first objective response (CR or PR), confirmed at the next tumor scan, and the date of documented disease progression per RECIST v1.1 or death, whichever comes first. Patients who do not experience objective CR or PR will not be included in the analysis. For patients with objective response who do not reach radiographically determined PD or die at the time of analysis, censored time will be calculated following the rules detailed in Section 12.4.6.2. The median, 25th percentile and 75th percentile will be estimated using the Kaplan-Meier method with their corresponding 95% CI calculated based on the method by Brookmeyer and Crowley (1982).

OS:

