Tumor response criteria will be based on RECIST v1.1 (Eisenhauer, 2009) as cited in Section 17.4. A partial or complete response should be confirmed by a repeat scan not less than 4 weeks from the date the response was first documented per RECIST v1.1.

G1T28-213

For those patients who have not progressed clinically or radiologically at the time of study drug discontinuation, every effort should be made to continue radiological tumor assessments, utilizing the same imaging modality as used at Screening.

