# **Analysis for Tumor Responses**

At each tumor assessment visit, an overall time point response by RECIST v1.1 will be derived programmatically using the measurements provided by the Investigator for target lesions, non-target lesions, and new lesions collected in the eCRF. Best overall response (BOR) will be determined using all visit responses prior to or on the date of (i) radiographic disease progression; (ii) withdrawal of consent to obtain tumor scans; (iii) death; (iv) lost to follow-up; or (v) initiation of subsequent anticancer therapy, whichever is earlier.

The number and percentage of patients in each category of derived BOR (confirmed complete response (CR), confirmed partial response (PR), stable disease (SD), PD, or Not Evaluable) will be summarized.

ORR is defined as the proportion of patients with BOR of confirmed CR or confirmed PR. ORR, along with its exact 95% two-sided CI using the Clopper-Pearson method, will be computed. ORR will be analyzed based on the RE population.

CBR is defined as the proportion of patients with a BOR of confirmed CR or confirmed PR or SD lasting 24 weeks or longer from the first date of study drug administration. The analysis of CBR will be performed using the methods similarly to ORR.

DOR is the time between first objective response of CR or PR (confirmed) and the first date that progressive disease is documented or death, whichever comes first. DOR will only be analyzed for the patients who have achieved objective response. For patients with objective response but did not reach radiographically determined PD or died, the last adequate tumor assessment date prior to the earliest time of the following will be used to calculate censored time: (i) withdrew consent to obtain scans; (ii) lost to follow-up; (iii) initiated subsequent anticancer therapy. The Kaplan-Meier method will be used to estimate the median, 25%, and 75% percentile of DOR, along with the 95% CI, which is calculated using the method by Brookmeyer and Crowley (1982).

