8.2.3. Analysis for Secondary Endpoints - Anti-tumor Efficacy Endpoints

The analysis for BOR, CBR, and ORR (see variable definitions in Section 8.1.2) will be based on the RE population.

Tumor response status classified by BOR will be tabulated with the number and percentage of patients in each category of CR, PR, SD, PD or NE, where the percentages are calculated based on the number of patients in the RE population.

ORR along with its exact 95% two-sided CI using the Clopper-Pearson method will be computed.

Confirmed ORR and CBR will be summarized and analyzed using the same methods as are used for the ORR.

For patients who achieved CR or PR as BOR status, DOR will be analyzed. The Kaplan-Meier method will be used to estimate the median, 25% and 75% percentile of DOR, along with its 95% CI calculated using the method by Brookmeyer and Crowley (1982).

Data listings will include tumor scan data, Investigator determined timepoint responses and BOR, and programmatically derived tumor response status, and confirmed tumor response status.

G1 Therapeutics

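### SAP 8.1.2 gives the label ORR to an unconfirmed response rate, against SAP Table 1 and the protocol; 8.2.3 also drops confirmation from the BOR table and the DOR population, and Section 10 declares none of it

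*SAP*

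**What the plan says.** The protocol makes confirmation part of the endpoint. Its Synopsis counts patients with a "best overall response (BOR) of either confirmed complete response (CR) or confirmed partial response (PR) per RECIST v1.1". Table 5 carries the same requirement, and Section 12.4.6.2 states: "ORR is defined as the proportion of patients with BOR of confirmed CR or confirmed PR". Section 11.2.1 supplies the scan rule: "A partial or complete response should be confirmed by a repeat scan not less than 4 weeks from the date the response was first documented".

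The SAP starts in agreement. Table 1 in Section 1.2 reads: "ORR defined as the percentage of patients with BOR of confirmed CR or confirmed PR per RECIST v1.1".

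Section 8.1.2 then departs from it. Its list of secondary anti-tumor endpoints contains BOR, ORR, CBR and DOR, and the ORR rule is: "Achieving an objective response for a patient is defined as having a CR or PR as the BOR". The BOR categories there carry no confirmation requirement. A separate subsection adds: "Confirmed ORR (confirmed CR or PR) is defined as the proportion of the patients who achieved confirmed objective response".

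Section 8.2.3 covers the analysis: "The analysis for BOR, CBR, and ORR (see variable definitions in Section 8.1.2) will be based on the RE population". It continues: "Confirmed ORR and CBR will be summarized and analyzed using the same methods as are used for the ORR".

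**The concern.** The SAP names two rates, and the one carrying the label of the listed secondary endpoint is not the one that Table 1 and the protocol define. Because 8.2.3 sends the ORR analysis back to the definitions in 8.1.2, the output labelled ORR follows the unconfirmed rule.

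Two further sentences in 8.2.3 drift the same way. The BOR table loses the confirmed categories that the protocol tabulates, and the DOR analysis is described for anyone with CR or PR as BOR.

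Response is derived from investigator measurements in an open-label, single-arm study, so the confirming scan is one of the few safeguards built into the endpoint. A reader of the study report who takes ORR to mean what the protocol says could be reading a higher rate, and a DOR estimate that includes patients who should have no DOR value.

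**Working it through.** The question is one of definition, so the first step is to set the places side by side.

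| Quantity | Protocol | SAP Table 1 | SAP 8.1.2 | SAP 8.2.3 |
|---|---|---|---|---|
| ORR | Confirmed (Synopsis, Table 5, 12.4.6.2) | Confirmed | Not confirmed | Refers to 8.1.2 |
| Confirmed ORR | This is the ORR | This is the ORR | Separate quantity, not in the endpoint list | Same method as ORR |
| BOR table | CR and PR confirmed (12.4.6.2) | – | Categories without confirmation | Categories without confirmation |
| DOR population | Confirmed responders (Synopsis, 12.4.6.2) | Not specified | Confirmed responders | CR or PR as BOR |
| CBR | Confirmed CR or PR, or SD of at least 24 weeks | Confirmed | Confirmed | Same method as ORR |

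**Could plain ORR be shorthand for the confirmed rate?** No. If it were, the subsection on confirmed ORR, with its own 4-week interval, would be redundant. Section 8.2.3 treats ORR and confirmed ORR as two results, and its listings carry derived response status and confirmed response status as separate items.

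**Does the precedence rule settle it?** SAP Section 1 lets the SAP override the protocol. That cannot resolve a conflict inside the SAP: Table 1 against 8.1.2 for ORR, and 8.1.2 against 8.2.3 for DOR.

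**Is it declared?** Section 10 lists the closed enrollment, the merged analyses, the dropped myeloprotection endpoints, the ECOG output and the laboratory change summaries. Its only mention of tumor response concerns timing.

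**Direction.** On the same response evaluable (RE) population, confirmed responders are a subset of all responders, so the figure labelled ORR is never below the protocol ORR.

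**Size.** The plan states no ORR assumption or precision target, so there is no figure of its own to reproduce. Its power calculation concerns PFS only and is unaffected. The inputs for an example are:

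- n = 30, the final enrollment (SAP 1.1 and 10), taken as the RE count. This is an assumption, because no RE count is given; n = 25 is used as a lower assumed value.
- 10 responders, from the 33.3% ORR that Protocol 4.1 cites for sacituzumab govitecan-hziy: 0.333 × 30 = 9.99. The protocol does not say whether that 33.3% is a confirmed rate.
- 0 to 3 of the 10 unconfirmed. This is also an assumption.

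The shift per unconfirmed responder is 1/n: 1/30 = 3.3 points, or 1/25 = 4.0 points.

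The exact 95% limits for x responders out of n (Clopper-Pearson) are the 0.025 quantile of Beta(x, n − x + 1) and the 0.975 quantile of Beta(x + 1, n − x).

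| Unconfirmed | Figure labelled ORR (8.1.2) | Protocol ORR | DOR set, 8.2.3 | DOR set, 8.1.2 |
|---|---|---|---|---|
| 0 | 10/30 = 33.3% (17.3–52.8) | 10/30 = 33.3% (17.3–52.8) | 10 | 10 |
| 1 | 33.3% (17.3–52.8) | 9/30 = 30.0% (14.7–49.4) | 10 | 9 |
| 2 | 33.3% (17.3–52.8) | 8/30 = 26.7% (12.3–45.9) | 10 | 8 |
| 3 | 33.3% (17.3–52.8) | 7/30 = 23.3% (9.9–42.3) | 10 | 7 |

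**The case against.** The strongest reply is that nothing is lost. Confirmed ORR is defined with the same 4-week interval as the protocol, analysed by the same exact method, and listed by patient. Both rates will appear under distinct names, and the only open question is which of them is called the secondary endpoint. This stands, and it limits the harm. It does not remove the contradiction with Table 1.

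On DOR, the endpoint list, the subsection heading and the definition in 8.1.2 all say confirmed, so the sentence in 8.2.3 may simply be loose wording. That is plausible. Read literally, though, the two sections give different populations, and a programmer cannot follow both.

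On CBR, the definition keeps confirmation. Only a literal reading against the unconfirmed BOR categories could leave out a patient with an unconfirmed PR and disease control beyond 24 weeks. This may never occur, and the point does not rest on it.

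On size, the counts in the example are assumed, and the 33.3% comes from another study without trilaciclib. That is correct. Only the 1/n step is free of an assumed responder count, and even it needs an RE denominator.

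Finally, ORR is descriptive, with no test or threshold attached, and the analysis supports an abbreviated report. That also stands, and it keeps the point below the level of a flaw in a decision rule.

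**Conclusion.** The concern holds. As written, the SAP attaches the ORR label to a rate that can only match or exceed the endpoint in its own Table 1 and in the protocol. It tabulates BOR without the protocol's confirmed categories, gives two different DOR populations, and declares none of this as a change.

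The numerical effect is unknown and may be zero. It is 3.3 points per unconfirmed responder at an assumed RE count of 30 and 4.0 points at 25. In the example with three unconfirmed among ten responders, the reported figure is 33.3% against 23.3%. The consequence is a mislabelled secondary estimate and an undetermined DOR set. The primary PFS analysis is not affected. The correction should be made, but the trial's main conclusion does not depend on it.

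**What to change.** - In SAP 8.1.2 and 8.2.3, name confirmed ORR on the RE population as the secondary endpoint, in line with Table 1 and Protocol 12.4.6.2. Label the unconfirmed rate as supportive.
- In 8.2.3, insert confirmed in the sentence that sets the DOR population.
- Tabulate BOR and derive CBR from confirmed response, as in Protocol 12.4.6.2. State which remaining BOR category an unconfirmed response falls into; the 5-week minimum for stable disease already in 8.1.2 must be applied consistently with that rule.
- Add a line to Section 10 recording the unconfirmed rate as an addition to the protocol's analyses.

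The cost is a few sentences in two SAP sections and one line in a third, with matching edits to the table shells. No new data are needed. The one drawback for the sponsor is that the rate reported as ORR may be lower.
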